	
cost=£600/day). Including the cost of a second CTO PCI procedure (combined day-case –ordinary elective spell) £6933 (9, 17), the overall cost can total to £10,000. In contrast, the cost of a CTCA is £360 (as per local billing). Financial costs are one part of the issue, but a second CTO PCI procedure can also heighten patient anxiety and discomfort which are well known in patients prior to any PCI.
 
A feasibility study will help establish the role of a CTCA prior to CTO PCI to positively influence strategy and/or outcomes.

Objectives	
Primary:
 
i) Does performing a CTCA prior to CTO PCI improve the success of the CTO procedure?
 
Secondary:
 
i) To determine if CTCA prior to CTO PCI results in improved angina as determined using the Seattle Angina Questionnaire (SAQ) by SAQ.
 
ii) To determine if CTCA prior to CTO PCI reduces the need for a second procedure (due to improved procedural success rate).
 
iii) To assess if there are procedural differences between the intervention arm (CTCA) and usual care arm

Comparators	CTCA versus no CTCA prior to CTO PCI
Trial design	Randomised (1:1), prospective, single centre study
Methods (see figure 1)	
Study setting	Sandwell and West Birmingham NHS Trust, Birmingham, United Kingdom
Eligibility Criteria	
Inclusion Criteria:
 
Patients meeting all the below criteria will be included
 
 • ≥18 years • CTO with J-CTO score≥2 • Appropriate indication for CTO PCI • Adequate CTCA images for analysis 
Exclusion criteria:
 
Patients meeting any of the following criteria will be excluded
 
 • <18 years of age • CTO with J-CTO score<2 • Inadequate/degraded CTCA images • Pregnant/lactating women • Patients with severe contrast allergy • Patients unable to provide written informed consent

Intervention	
Experimental group: CTCA prior to CTO PCI Conventional group: CTO PCI
 
Patients will be randomised to CTCA or no CTCA prior to CTO PCI (figure 1)

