Outcomes	
Outcomes
 
Primary endpoint
 
 i. CTO PCI success rate in CTCA arm versus no CTCA arm 
Secondary endpoints
 
 i. Angina by the SAQ summary score at 6 months ii. Compare the number of patients who required a second CTO PCI procedure in the CTCA arm versus no CTCA arm iii. Procedural differences between the intervention CTCA arm versus no CTCA arm including: 
 a) Health Economics: 
 • Cost saved per patient due to improved success and reduction in readmission or further procedure b) CTO PCI efficiency: 
 • Wire crossing time • Procedure time c) CTO PCI safety outcomes: 
 • Procedural complications (Ellis perforation, tamponade, acute kidney injury/contrast induced nephropathy, access site bleeding, donor vessel injury) • Radiation: CTCA dose, CTO PCI dose, and combined CTCA and CTO PCI dose • Contrast: CTCA volume, CTO PCI volume, and combined CTCA and CTO PCI volume d) Change in CTO PCI strategy hierarchy as a result of the CTCA review
Participant/project timeline	Please see figure 2
Sample size	This is a feasibility study- to ensure completion within a year, we have estimated 20 patients, randomised 1:1 to each arm (10 patients per arm) as a sample size in a moderate size hospital which performs approximately 100 CTO PCIs annually
Intervention assignment	Block randomisation with sealed envelope technique
Data collection, management and analysis	
 • eCRF and online database to collect demographic, procedural and SAQ information

	
 • SAQ summary score at 6 months post PCI • Blood samples pre and post PCI • Comparison of demographics, procedural details, procedural success and complications, bloods, SAQ, and financial cost between the CTCA and non-CTCA groups • Categorical variables will be presented as percentage and compared with the chi square or Fisher's test • Continuous variables will be presented as median (range) and compared with student's t-test or Mann Whitney test. • In addition, modelling will be performed by binary logistic regression analysis to predictors of CTO PCI success.
Monitoring	CTO PCI procedural adverse events will be reported as usual on the national database and this data will be collected in the eCRF.

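### The between-arm test of the 6-month SAQ score uses no baseline score; adjusting for one is an optional precision gain, on average, if the baseline-to-6-month correlation exceeds about 0.26

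*Combined protocol and SAP*

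**What the plan says.** The first secondary objective is "To determine if CTCA prior to CTO PCI results in improved angina as determined using the Seattle Angina Questionnaire (SAQ) by SAQ". The matching endpoint under Outcomes is "Angina by the SAQ summary score at 6 months", which is a score at one time point and not a change.

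Under Data collection, management and analysis:

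- The only SAQ time point named is "SAQ summary score at 6 months post PCI". The next item in that list asks for bloods both before and after PCI.
- Data capture is described as "eCRF and online database to collect demographic, procedural and SAQ information", with no visit attached to the SAQ part.
- SAQ is among the variables compared between arms: "Comparison of demographics, procedural details, procedural success and complications, bloods, SAQ, and financial cost between the CTCA and non-CTCA groups".
- The method is "Continuous variables will be presented as median (range) and compared with" Student's "t-test or Mann Whitney test". Neither test takes a covariate.
- The only model is for a different outcome: "modelling will be performed by binary logistic regression analysis to predictors of CTO PCI success".

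The participant timeline is deferred to Figure 2, which is not shown in the text available to us.

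**The concern.** With 10 patients per arm, the interval for the SAQ difference will be very wide. The sample size was set by what can be completed in a year, so more patients are not on offer. A pre-randomisation SAQ is the obvious covariate for a 6-month SAQ. Using it can recover some precision from the same patients, provided the two scores are at least moderately correlated. If no baseline is recorded, it cannot be recovered later, so the choice has to be made before the first patient is randomised.

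What is at stake is the width of an interval on a secondary endpoint. The primary endpoint is not affected.

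**Working it through.** **Nothing to reproduce.** The plan gives no SAQ standard deviation, effect size, alpha, power or interval.

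**Inputs from the plan.** N = 20, randomised 1:1, 10 per arm (Sample size). Unadjusted two-sample comparison (Data collection, management and analysis).

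**Assumptions, not in the documents.** Two-sided 95% interval; baseline and 6-month scores roughly normal and linearly related with correlation r; all 20 patients give a 6-month score. The outcome SD is set to 1, since it cancels in the ratios.

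**1. Unadjusted half-width.** t(0.975, 18 df) × √(2/10) = 2.1009 × 0.4472 = 0.94 SD (root mean square). The mean over simulated trials is 0.93 SD.

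**2. ANCOVA variance relative to unadjusted.** The factor is (1 − r²) × (1 + 1/16). The 1/16 is the expected penalty for chance baseline imbalance, 1/(N − 4).

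**3. Ratio of interval widths.** √(variance factor) × t(17 df)/t(18 df), with 2.1098/2.1009 = 1.004 for the lost degree of freedom.

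| r | Variance factor | Equivalent multiple of patients (1/factor) | Width ratio | Mean half-width, simulated (SD) | Adjusted interval wider, % of trials |
|---|---|---|---|---|---|
| 0 | 1.0625 | 0.94 | 1.035 | – | 80 |
| 0.3 | 0.967 | 1.03 | 0.987 | 0.91 | 52 |
| 0.5 | 0.797 | 1.25 | 0.896 | 0.83 | 20 |
| 0.7 | 0.542 | 1.85 | 0.739 | 0.68 | 3 |

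The last two columns come from simulation of 200,000 trials per correlation. The simulated ratios of mean width were 1.033, 0.986, 0.895 and 0.738, in line with the formula.

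**4. Break-even.** Setting the width ratio to 1 gives r = √(1 − (16/17) × (2.1009/2.1098)²) = 0.258. With 9 or 8 patients per arm giving 6-month scores, it rises to 0.277 or 0.300. Break-even holds on average only: at r = 0.26 the adjusted interval is still the wider one in about 58% of single trials.

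**5. What it means for detection** (noncentral t, two-sided 5%). The difference detectable with 80% power goes from 1.325 SD unadjusted to 1.307, 1.187 or 0.979 SD at r = 0.3, 0.5 or 0.7. Power for a true difference of 0.5 SD goes from 18.4% to 18.8%, 21.8% or 29.9%.

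**The case against.** The strongest case against acting is that the plan contains no error here and no conclusion is likely to change. The endpoint is secondary, and the study makes no claim to power for it. Even at r = 0.7 the detectable difference is about 1 SD. The whole benefit depends on a correlation that the documents do not give. It may be low, because both arms undergo a procedure meant to change angina between the two measurements. This stands, and it is why the point is optional.

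The normality assumption is also open to challenge. The plan itself presents medians and allows Mann-Whitney, so non-normal scores are contemplated. In a simulation with an assumed ceiling (half of control-arm scores at the maximum, underlying correlation 0.5, underlying difference 0.5 SD), power was 13.1% for ANCOVA, 12.1% for the t-test and 13.6% for Mann-Whitney. Most of the power gain disappears there. This stands as a limit on the size of the benefit.

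Four stronger readings are tempting, and the documents do not support them:

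- **That no baseline SAQ is collected.** The eCRF item for SAQ has no time point and Figure 2 is not shown, so the text cannot settle this.
- **That the objective's reference to improved angina requires a change score.** The objective asks whether CTCA leads to better angina, and a between-arm comparison of 6-month scores addresses that.
- **That adjustment helps in every trial above 0.26 and never below it.** The threshold is an average, as the last column of the table shows.
- **That the planned comparison is assured to be unbiased with 5% type I error.** That could be said only if all randomised patients are analysed. Eligibility Criteria requires adequate CTCA images and excludes degraded ones. If images are first obtained after randomisation, this could remove patients from the CTCA arm only. ANCOVA would not correct such selective exclusion.

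**Conclusion.** The point holds as an optional precision improvement. No stated analysis uses a baseline SAQ, and on average baseline-adjusted ANCOVA would beat the stated t-test for interval width once the correlation exceeds about 0.26. The expected gain is negligible at 0.3, modest at 0.5 and useful at 0.7; the expected loss at zero correlation is about 3%. These figures rest on roughly normal, linearly related scores, complete 6-month follow-up and a two-sided 95% interval. The correlation range is assumed. The endpoint remains exploratory at 20 patients whichever analysis is used.

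**What to change.** 1. Confirm that an SAQ is recorded at consent, before randomisation, in all patients, or add one. If it is already recorded, only the analysis wording changes.
2. State that the 6-month summary score will be analysed by ANCOVA with arm and baseline SAQ, reporting the adjusted mean difference with its 95% confidence interval.
3. Keep Mann-Whitney on the 6-month score as a sensitivity analysis.
4. Label the endpoint exploratory.

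Cost: if no baseline is taken now, one short questionnaire of a few minutes per patient, entered in the planned eCRF. The Appendix costing already covers a fellow for consent and telephone follow-up. Beyond that, the cost is a line or two of analysis text and one degree of freedom. The downside is little or no gain, or a slightly wider interval, if the correlation turns out to be low.

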	
reconstruction of the fully occluded artery.
 
Angiographically, the CTO artery usually shows a short proximal portion of dye filled artery prior to the occlusion. In most patients there are some collaterals from the contralateral coronary artery which try to fill part of the occluded CTO artery. However the actual body of the CTO is not visible angiographically.
 
Computed Tomography Coronary Angiography (CTCA) can delineate the coronary anatomy in 3-dimensions, determining atherosclerotic plaque and occlusion location, severity and morphology. This makes it an attractive modality to assess the coronary CTO. Development of a CTCA based complexity score for stratifying CTOs by difficulty resulted in the CT-RECTOR score (Computed Tomography Registry of Chronic Total Occlusion Revascularization, table 1)(16). Variables included in this score are multiple occlusions, blunt stump, severe calcification, bending, duration of CTO ≥ 12 months and previously failed PCI (all scored 1). The CT-RECTOR score correlates with the J-CTO score and has a better area under ROC curve (ROC AUC 0.83 for CT-RECTOR score and 0.71 for J-CTO, $p < 0.001$) and predicts CTO PCI success (16)
 
The role of routine CTCA pre-CTO PCI is as yet undefined as current practice involves the use of CTCA in patients who have had an unsuccessful CTO PCI attempt or previous coronary artery bypass grafting (CABG).
 
Need for a feasibility study:
 
Current practice at our centre involves the use of CTCA in patients who have had an unsuccessful CTO PCI attempt or previous coronary artery bypass grafting (CABG) but the role of routine CTCA pre-CTO PCI is as yet undefined.
 
The small additional investment of a CTCA could help plan/improve a complex procedure and may reduce the need for additional procedures and readmissions.
 
The mean acute treatment cost of a CTO PCI is approximately (combined day-case –ordinary elective spell) £6933 (9, 17) whereas the approximate cost of a CTCA is £360 (as per local billing). Elective readmission for a failed CTO PCI procedure would entail an additional financial (to the provider) and emotional cost (to the patient).
 
The cost of an additional CTO PCI procedure aside, readmission and bed charges themselves can reach £1000/day (readmission =£255/day)(17)and bed

--	---

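### Continuous outcomes are shown only as median (range), yet a t-test of unreported means is allowed; the effect is small for most outcomes but can reverse the per-patient cost result

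*Combined protocol and SAP*

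**What the plan says.** The Synopsis row on data collection, management and analysis has one rule for continuous variables: "Continuous variables will be presented as median (range) and compared with student's t-test or Mann Whitney test". It gives no criterion for choosing between the two tests.

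The same row sets the scope of the comparisons: "Comparison of demographics, procedural details, procedural success and complications, bloods, SAQ, and financial cost between the CTCA and non-CTCA groups". The Outcomes row adds the continuous endpoints: "Angina by the SAQ summary score at 6 months", wire crossing and procedure time, radiation dose and contrast volume (each for CTCA, for CTO PCI and combined), and a health-economics endpoint, the cost saved per patient through better success and fewer readmissions or repeat procedures.

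No mean, SD, quartiles, between-arm difference or confidence interval is planned for any of these. The primary endpoint, "CTO PCI success rate in CTCA arm versus no CTCA arm", is binary and is not covered by this rule.

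**The concern.** If the t-test is used, the p-value refers to a difference in means that the reader never sees, printed beside medians that may tell a different story. The test is also left open, so it can be chosen once the data are visible.

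The consequence depends on the outcome. Where the distribution is roughly symmetric, or the interest is in a typical patient, the median is a reasonable summary. A saving per patient is different: it is total cost divided by number of patients, so it is a mean by definition. Most patients have one procedure and a minority have an expensive second one. The median ignores that minority, and the minority is where any saving from CTCA would arise.

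**Working it through.** **Inputs from the protocol.** 20 patients randomised 1:1, so 2 × 10 = 20, which agrees with the stated total. CTO PCI £6,933; CTCA £360; up to £10,000 for a readmission including the second procedure (Synopsis, description of the research question). The plan states no alpha, power, SD or distribution, so there is no power calculation to reproduce. The distributions and repeat counts below are assumptions.

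**1. The t-test beside medians.** A made-up set with 10 values per arm:
- Arm A: 30, 35, 40, 45, 50, 52, 60, 70, 150, 210. Median 51, mean 74.2.
- Arm B: 32, 36, 42, 46, 50, 52, 58, 62, 66, 70. Median 51, mean 51.4.
- t-test p = 0.25; Mann-Whitney p = 0.88.

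The medians are identical, so the planned table would not show the 22.8-unit difference in means that the t-test examines.

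**2. How often this misleads.** Simulation, 40,000 trials per setting, 10 per arm:

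| Setting | Opposite signs of mean and median difference | t-test p < 0.05 and opposite signs | Tests disagree at 0.05 | Smaller p < 0.05 |
|---|---|---|---|---|
| Normal, no difference | 17.7% | 0 | 2.0% | 5.8% |
| Log-normal (log SD 0.8), no difference | 24.5% | 0 | 2.9% | 5.5% |
| Normal, shift 0.8 SD | 5.0% | 0 | 7.6% | 41.0% |
| Log-normal, shift 0.5 on the log scale | 11.3% | 0 | 10.2% | 26.7% |

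In a separate run with no true difference, the typical p-value in trials with opposite signs was 0.79 (normal) and 0.73 (log-normal, log SD 0.6). The two tests used alone rejected in 3.9-5.2% of trials with no difference, so choosing the smaller p-value adds little.

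**3. Cost saved per patient.** Let r0 and r1 be the proportions needing a repeat in the no-CTCA and CTCA arms, and R the cost of a repeat.
- Mean saving = R × (r0 − r1) − 360.
- Median saving = −360 whenever fewer than half of each arm need a repeat, because both medians then fall on single-procedure patients.

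Assume 2 of 10 versus 0 of 10 repeats, with R = £6,933:
- No-CTCA mean = (8 × 6,933 + 2 × 13,866)/10 = £8,319.60; median £6,933.
- CTCA mean = median = 6,933 + 360 = £7,293.
- Mean saving = 8,319.60 − 7,293 = £1,026.60. Median saving = 6,933 − 7,293 = −£360.
- t-test: the SD is £2,923 in the no-CTCA arm and 0 in the CTCA arm, so SE = 2,923/√10 = 924, t = 1,026.60/924 = 1.11 on 18 df, p = 0.28.
- Mann-Whitney: each CTCA patient costs more than 8 of the 10 controls, so U = 80 against 50 expected. The tie-corrected SD is 11.92, z = (30 − 0.5)/11.92 = 2.47, p = 0.013, in the direction of CTCA being dearer.

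With 3 versus 1 repeats the mean saving is again 0.2 × 6,933 − 360 = £1,027 and the median again −£360. Charging £10,000 per repeat with 2 versus 0 gives a mean saving of 0.2 × 10,000 − 360 = £1,640; the median is still −£360. At £6,933 the mean breaks even at r0 − r1 = 360/6,933 = 5.2 percentage points.

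**4. The missing SD.** For 10 normal values the expected range is 3.078 SD, so range/3.078 estimates the SD with a coefficient of variation of 26%, against 24% for the sample SD. Even a reported single-arm SD (9 df) has a 95% CI from 0.69 to 1.83 times the estimate.

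**The case against.** The analysis sentence is a common synopsis line naming a parametric and a non-parametric option. Medians with Mann-Whitney are a conventional pairing, so there is no mismatch if that test is used. This stands, and the point is limited to the t-test option, with cost as the exception because there the median itself is the wrong summary.

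A reader might infer from the 18-24% sign disagreement with no true difference that significant results will often contradict the medians shown. They will not: none of the simulated trials above with t-test p < 0.05 had opposite signs. Nor is the open choice of test a serious source of false positives, at 5.5-5.8% for secondary outcomes.

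A reader might also infer that the trial fails to deliver its main planning number, or that a range is useless for planning. Neither is supported. The stated purpose is "A feasibility study will help establish the role of a CTCA prior to CTO PCI to positively influence strategy and/or outcomes", no objective promises an SD, and the primary endpoint needs none. For near-normal data the range recovers the SD almost as precisely as the sample SD does, and 10 per arm is the larger limit.

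On cost, it is fair to say that the repeat counts are invented and that every patient is given the same tariff. With real variation in cost between patients, the median gap would not be exactly £360 and the Mann-Whitney result could be much weaker. What stands is that the median leaves out the cost of repeats when they affect a minority.

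**Conclusion.** The point holds as a minor one about reporting and pre-specification. The plan allows a test of means while showing no means, and does not say which test applies where. For SAQ, times, dose and contrast the practical effect is small.

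For the cost saved per patient the rule can give the wrong direction. At the protocol's prices and fewer than half of each arm needing a repeat, the medians show CTCA £360 dearer even when it saves about £1,027 per patient on average. In that example the two permitted tests give p = 0.28 and p = 0.013, the latter against CTCA. This rests on assumed repeat counts (2 versus 0), uniform tariff costs and £6,933 per repeat; it illustrates the rule and is not a forecast of the result. Neither the primary endpoint nor the sample size is affected.

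**What to change.** Replace the sentence on continuous variables with a rule by outcome:

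- **All continuous outcomes:** report n, mean (SD) and median (quartiles) by arm. Name one test per outcome before any data are seen, and give the between-arm difference that this test addresses, with a 95% CI.
- **Cost and SAQ summary score:** arithmetic mean difference.
- **Procedure time, CTO PCI and combined dose, CTO PCI and combined contrast:** one prespecified method, either the ratio of geometric means or the Hodges-Lehmann shift with Mann-Whitney.
- **CTCA dose and CTCA contrast volume:** describe in the CTCA arm only. The other arm has no planned CTCA, so no between-arm ratio or test applies.

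This changes wording in the analysis row only. It needs no new data or patients; the cost is a few more table columns.

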**Computed Tomography Coronary Angiography (CTCA) prior to Chronic Total Occlusion (CTO)
Percutaneous Coronary Intervention (PCI) - a feasibility study**

TRIAL SUMMARY

Trial Title	Computed Tomography Coronary Angiography (CTCA) prior to Chronic Total Occlusion (CTO) Percutaneous Coronary Intervention (PCI) - a feasibility study
Summary of Trial design	Randomised, prospective, single centre feasibility study of CTCA prior to CTO PCI
Site and Chief Investigator	Sandwell and West Birmingham NHS Trust, Birmingham, United Kingdom [name]
Participant population	Patients undergoing CTO PCI
Planned sample size	20
Number of sites	1
Intervention duration	Prior to index CTO PCI procedure
Follow up duration	6 months
Planned trial duration	1 year
Primary objective	To determine if CTCA prior to CTO PCI results in improved procedural success rate?
Secondary objectives	i) To determine if CTCA prior to CTO PCI results in improved angina as determined by Seattle Angina Questionnaire (SAQ)? ii) To determine if CTCA prior to CTO PCI reduces the need for a second procedure due to improved procedural success rate? iii) Are there procedural differences between the intervention arm (CTCA) and usual care
Intervention	Randomised to CTCA versus no CTCA prior to CTO PCI

ABBREVIATIONS:

CABG: Coronary Artery Bypass Graft

CAD: Coronary Artery Disease

CTCA: Computed Tomography Coronary Angiogram

CTO: Chronic Total Occlusion

J-CTO: Japanese Chronic Total Occlusion

PCI: Percutaneous Coronary Intervention

QALYS: Quality Adjusted Life Years

QoL: Quality of Life

SAQ: Seattle Angina Questionnaire

Trial Protocol Synopsis

Item	Description

Title
	
Computed Tomography Coronary Angiography (CTCA) prior to Chronic Total Occlusion (CTO) Percutaneous Coronary Intervention (PCI)

Introduction
	

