
Description of research question
	
Null Hypothesis: CTCA performed prior to CTO PCI will not improve procedural success
 
Existing knowledge: A chronic total occlusion (CTO) is present in 15-20% of patients with angina who are referred for coronary angiography. Due to the complexity of occlusive coronary artery disease (CAD), including a high prevalence of calcium and tortuosity within long segments of disease, CTO PCI is associated with higher procedural complication rates (11). Inability to detect the intraluminal path in the CTO artery, combined with calcification and tortuosity can result in unsuccessful guidewire crossing and procedural failure. Successful CTO PCI has been shown to improve Quality of Life (QoL) at 12 months(4). These patients are more likely to be angina free at 12 months (5, 6) as assessed by the Seattle Angina Questionnaire (SAQ) (7, 8). CTO PCI in symptomatic patients is cost effective and results in greater quality-adjusted-life-years (QALYS)(9, 10).
 
CTO percutaneous coronary intervention (PCI) procedure success rates increased from 68% to 79% between 2000 and 2011, and are as high as 90% when performed by high-volume CTO operators (2, 3). Complexity of the CTO is determined by several factors and several CTO complexity scores, derived from (invasive) angiographic lesion and clinical characteristics, have been shown to correlate with procedural success and complication rates (JCTO(12), PROGRESS(13), RECHARGE(14), Euro-CASTLE(15)). The most commonly utilised score is the J-CTO (Multicenter Chronic Total Occlusion Registry of Japan)(12) which assigns a score of 1 each to the angiographic CTO proximal cap (tapered or blunt), calcification, tortuosity (>45°), lesion length (≥20mm) and previous failure, with a maximum score =5. Scores ≥2 are considered CTOs that are difficult to perform and require advanced techniques for successful revascularisation.
 
In a proportion of these patients, the first procedure either fails completely or partially succeeds in forming a tract within the occluded artery but this is inadequate for stent delivery and the patient requires a second procedure, occasionally a third for complete success and

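### Efficacy is the only primary question at 10 per arm, yet no confidence interval is planned, and the added logistic regression can have no finite estimate

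*Combined protocol and SAP*

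**What the plan says.** The Trial Summary gives the primary objective as "To determine if CTCA prior to CTO PCI results in improved procedural success rate". The null hypothesis, under Description of research question, is that "CTCA performed prior to CTO PCI will not improve procedural success". Objectives and Outcomes list one primary objective and one primary endpoint, both about procedural success by arm. The rationale for a feasibility study ends: "A feasibility study will help establish the role of a CTCA prior to CTO PCI to positively influence strategy and/or outcomes".

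Under Sample size, 20 patients (10 per arm) are chosen so that the study finishes within a year. No alpha, power, effect size or precision target is given.

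Under Data collection, management and analysis, categorical outcomes are to be shown as percentages and compared by chi-square or Fisher test. Confidence intervals are not mentioned anywhere. The same section adds that "modelling will be performed by binary logistic regression analysis to predictors of CTO PCI success". It names no covariates, sets no limit on their number and gives no method for sparse data.

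The only success rates are in the background: "procedure success rates increased from 68% to 79% between 2000 and 2011", and they "are as high as 90% when performed by high-volume CTO operators". None is given for the trial's own population, lesions with a J-CTO score of 2 or more, which the text says "are considered CTOs that are difficult to perform and require advanced techniques for successful revascularisation".

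**The concern.** A small study is useful when it reports an estimate with its uncertainty. This plan asks an efficacy question, answers it with a test, and omits the uncertainty. If a non-significant result is the likely outcome whether or not CTCA works, the p-value says almost nothing, and the plan has neither an interval nor a caution to stop it being taken as absence of benefit.

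The regression raises a separate problem. What limits a logistic model here is the number of failures, not the 20 patients. With a handful of failures, one arm or one level of a covariate may contain none. Ordinary maximum likelihood then gives an infinite odds ratio, which software may print as a very large number and which could be reported as a predictor of success.

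**Working it through.** **Inputs.** From the documents: 10 per arm, and background success rates of 68%, 79% and 90%. Assumed: two-sided alpha of 0.05, and the pairing of those rates into usual care v CTCA. The plan's figure of 20 has no statistical inputs, so there is nothing to reproduce beyond 2 × 10.

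**Primary comparison.** All 11 × 11 = 121 possible outcomes were enumerated, each weighted by the product of two binomial probabilities.

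| Usual care v CTCA | 79 v 90% | 68 v 79% | 68 v 90% |
|---|---|---|---|
| Power, Fisher | 1.5% | 2.3% | 7.2% |
| Power, uncorrected chi-square | 5.3% | 6.4% | 16.9% |
| Observed difference reversed | 15.2% | 20.5% | 5.9% |
| Observed difference exactly zero | 20.2% | 17.3% | 10.5% |
| Zero or reversed | 35% | 38% | 16% |
| Mean width of Newcombe 95% CI (points) | 65 | 69 | 66 |

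With 9/10 successes after CTCA, Fisher reaches 0.05 only if usual care has 3/10 or fewer.

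Example of what an interval adds: 9/10 v 8/10. The Wilson limits are 0.596 to 0.982 and 0.490 to 0.943, and the difference is 0.10.
- Lower limit: 0.10 − √[(0.900 − 0.596)² + (0.943 − 0.800)²] = −0.24.
- Upper limit: 0.10 + √[(0.982 − 0.900)² + (0.800 − 0.490)²] = +0.42.

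Fisher gives p = 1.0 for this table. The interval shows that the data fit both a large benefit and a sizeable harm.

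**Failures available to the regression.** Expected failures = 10(1 − p₁) + 10(1 − p₂).
- 79 v 90%: 2.1 + 1.0 = 3.1.
- 68 v 79%: 3.2 + 2.1 = 5.3.
- 68 v 90%: 3.2 + 1.0 = 4.2.
- Equal rates: from 2.0 (90% in both arms) to 6.4 (68% in both arms).

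**Arm as the only term.** There is no finite odds ratio if either arm has 0/10 or 10/10 successes. At these rates 10/10 dominates.
- 79 v 90%: 0.79¹⁰ = 0.095 and 0.90¹⁰ = 0.349, so 1 − (1 − 0.095)(1 − 0.349) = 41%.
- 68 v 79%: 11%. 68 v 90%: 36%.
- Equal rates of 68, 79 and 90%: 4%, 18% and 58%.

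**Models with covariates.** These are simulations with a linear-programming check for separation. The covariates are illustrative, because the plan names none. Each of the five J-CTO items was assumed present independently with probability 0.3 or 0.5 and unrelated to success, and patients were kept if they scored 2 or more. Proportion with no finite estimate:

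| Model | 79 v 90% | 68 v 79% | 68 v 90% |
|---|---|---|---|
| J-CTO score, no arm | 15–36% | 4–16% | 7–23% |
| Arm + J-CTO score | 44–56% | 15–25% | 40–47% |
| Arm + five J-CTO items | 87–88% | 61% | 80–81% |

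**If difficult lesions fail more often (assumed rates).**
- Lower success in both arms, arm only: 50 v 70% (8 expected failures) gives 3.0%; 40 v 60% (10 expected failures) gives 1.2%.
- Usual care at 30 to 60% with CTCA held at 90%: 35 to 37%, nearly all of it from 0.90¹⁰ = 35%.
- Arm plus five items at 50 v 70%: about 40 to 50%.
- Fisher power: 5.5% at 50 v 70%, and 15 to 67% for 60% down to 30% v 90%.

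**The case against.** The study is called feasibility throughout, claims no power and explains its size by practicality. That stands: a reader might infer that 20 patients is an error, but the documents make no promise that 20 patients would break.

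Percentages per arm will be shown, so any reader could compute an interval, and nothing in the documents says that a non-significant result will be reported as no benefit. Both statements are true. The absence of an interval biases no result. It leaves the sole primary analysis without a stated measure of precision when the question is posed as efficacy, and that is an omission in the plan.

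The objection to the regression figures has more force. The plan does not say that arm is in the model, and the five-item model is an illustration. The background rates may also be too high for this population. A reader might infer that the regression will usually fail, or that lower usual-care success would not help. The documents support neither. The arm-only figure falls to 1 to 3% if success is lower in both arms, and stays near 35% only if the CTCA arm is near 90%. What survives is that a model for several predictors, with no cap and no sparse-data method, is not reliably supported even by 7 to 10 failures.

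**Conclusion.** The point holds in two parts, and should be fixed.

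- **Primary analysis.** Efficacy is the only primary question, and the plan gives a test without an interval. At the documents' own rates a non-significant p-value is expected in about 93 to 98% of trials by Fisher (83 to 95% by uncorrected chi-square) even when CTCA helps. This rests on alpha of 0.05 and on background rates that are not specific to J-CTO scores of 2 or more. If usual-care success is much lower and CTCA success near 90%, the result is less one-sided.
- **Regression.** It is unspecified and can have no finite estimate. At the background rates the figures are 11 to 41% for arm alone (4 to 58% with equal rates), about 4 to 36% for J-CTO score without arm, and about 61 to 88% for the illustrative six-term model. The arm-only figures are exact for the stated rates. The covariate figures depend on assumed prevalences, independence and no effect, and show scale only.

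The concern is not that the trial is too small to run. It is that the objective and the analysis claim a kind of answer that 20 patients can rarely give.

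**What to change.** 1. Report success in each arm and the difference with one pre-named 95% confidence interval (for example Newcombe), as an estimate to inform a later trial. State that a non-significant result is not evidence of no benefit, and make no efficacy claim from the interval or from a p-value.
2. Preferably delete the logistic regression and tabulate success by arm and J-CTO score. If a model is kept, limit it to a Firth-penalised model with arm and J-CTO score, labelled exploratory. Its estimates will be finite but should be expected to be very imprecise.
3. Reword the primary objective and the null hypothesis as estimation of success by arm, so that they match the analysis.

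Cost: the same 20 patients and no new data, since the J-CTO score is already needed for eligibility. This goes beyond editing, because the stated primary objective changes. The trial gives up a formal efficacy claim and a predictor model that it could rarely have supported.
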